4.4 Patient NK cell infusion and CpG administration plan

This treatment regimen may be administered on an outpatient basis.

4.4.1 NK cell-enriched DLI:

The target cell dose for NK cell-enriched DLI will be as many cells as can be collected with less than 0.5×10^6 CD3+ CD56- cells/kg patient weight in the 4-6/8 HLA-matched related setting and 1×10^6 CD3+ CD56- cells/kg patient weight in the 7-8/8 HLA-matched related or unrelated setting. The first NK cell-enriched DLI will be administered between one to six months post-transplant. The second NK cell-enriched DLI will be administered one to three months post the first infusion, in patients who have < grade II aGVHD at the time of infusion and have not had unacceptable toxicities (see 6.2.1 Definition of unacceptable toxicity) that are at least possibly related to the previous DLI and resolved to grade 1 or less. The second DLI will NOT be administered in patient with \geq grade III aGVHD at the time of infusion or unacceptable toxicities at least possibly related to the first infusion. If patients have GVHD and were on immunosuppressive therapy at study entry, patients will continue on their stable dose of immunosuppressive agents started for therapy of acute GVHD before the NK cell-enriched DLI, and will not taper until at least 6 weeks following the each NK cell-enriched DLI (unless disease progression or patient toxicity from the agents requires earlier taper). The donor NK cells will be infused over 30 minutes. Diphenhydramine 25 mg iv or po, and Acetaminophen 650 mg po will be used prior to each reinfusion, unless there is a history of allergy or contraindication in the patient, in which case hydrocortisone 50mg IV will be used.

These cells are infused into the patient via a peripheral intravenous line or central line. If signs of GVHD occur after NK cell-enriched DLI, immunosuppressive agents (prednisone, cyclosporine, tacrolimus and/ or mycophenolate preferred first choices) may be started.

4.42 Adverse effect of NK cell-enriched DLI:

We previously delivered 51 NK cell-enriched DLIs to 30 patients following a 3-6/6 HLA-matched T-cell-depleted nonmyeloablative allogeneic transplantation.⁸³ In this study, mild skin aGVHD was experienced by 2 of the 14 matched patients prior to treatment on this study (Table 2A). Six of these patients experienced equal to or greater than grade 1 aGVHD, although only 1 had grade 3-4 (severe) overall aGVHD. The median onset following the first NK cell infusion was 2 months (range: 1-7 months). Mild skin aGVHD was experienced by 4 of the 16 mismatched patients prior to enrollment in this study. At the doses provided, equal to or greater than grade 1 aGVHD was experienced by 8 of the 16 patients, with skin GVHD being common, although only 1 of the 16 had grade 3-4 (severe) overall aGVHD. The median onset of aGVHD following the first NK cell infusion was 1.5 months (range: 1-5 months). Only 1 case of severe chronic GVHD (cGVHD) was encountered. Severe non-aGVHD toxicity was uncommon (Table 2B). Only 1 subject in each group (matched and mismatched) had bacterial sepsis, although viral exanthemas remained a significant concern despite the lymphocyte infusions with Polyoma, cytomegalovirus (CMV), varicella zoster virus (VZV), herpes simples virus (HSV), and Parainfluenza all encountered. Three cases of cardiac dysrhythmias (atrial) needing medication for rate control were documented and 1 case of transient renal insufficiency. There was 1 case of significant decrease in donor engraftment, possibly leading to secondary graft failure, not because of evident disease progression.

Table 3:

Table 2. Toxicities for the Matched Sibling Donors, N = 14 (24 Total NK Cell-Enhanced Infusions); or Mismatched Family Member Donors, N = 16 (27 Total NK Cell-Enhanced Infusions)

(A) aGVHD								
Site ↓ / Grade →	HLA Matched N = 14 Patients; 24 Total Infusions				HLA Mismatched N = 16; 27 Total Infusions			
	1	2	3	4	1	2	3	4
Skin	1	1	2	—	3	3	1	—
Gut	2	—	—	—	2	—	—	1
Liver	—	—	1	—	—	—	1	—
Overall	2	3	1	—	4	3	—	1

(B) Non-GVHD toxicity								
Organ System ↓ / CTC Grade →	Matched			Mismatched			4/5	
	2	3	4	2	3			
Cardiac-arrhythmia	1	—	—	2	—	—		
Renal Insufficiency	—	—	—	1	—	—		
Infectious	—	—	—	—	—	—		
Polyoma cystitis	1	1	—	—	—	2		
CMV reactivation only	3	—	—	6	—	—		
CMV disease	—	—	—	—	1	—		
HSV	—	—	1	1	—	—		
Parainfluenza	—	2	—	—	3	—		
VZV	1	—	—	—	1	—		
Bacterial	—	2	1	2	2	—		1
Parasitic (ameba)	—	—	1	—	—	—		
Gastritis (non-GVHD)	2	—	—	—	—	—		
Hemolytic anemia	—	—	—	—	1	—		
Pulmonary (noninfectious)	1	—	—	—	—	—		
Posttransplant lymphoproliferative disorder (PTLD)	—	—	—	—	—	—		2

GVHD indicates graft-versus-host disease; VZV, varicella zoster virus; HSV, herpes simplex virus; CMV, cytomegalovirus; NK, natural killer.

One case of severe cGVHD noted in the mismatched group.

(Rizzieri DA, et al. Biol Blood Marrow Transplant. 2010 Aug;16(8):1107-14.)

4.5 DUK-CPG-001

Patients are randomized into two arms: patients who receive NK cell-enriched DLI alone and patients who receive NK cell-enriched DLI with DUK-CPG-001, an agent chemically identical to CPG 7909 and this data is what is presented below for potential toxicities.

4.51 DUK-CPG-001 preparation

DUK-CPG-001 (5'-TCGTCGTTTGTCTGGTTTGTCTGTT-3') was synthesized with a wholly phosphorothioate backbone in GMP facility of Agilent Technologies (Boulder, CO). Agilent Technologies produced DUK-CPG-001 that complies with the pharmaceutical GMP guidelines for use as active pharmaceutical ingredients (API) in clinical trials.

Bulk DUK-CPG-001 is resuspended in normal saline with a final concentration of 10 mg/mL, aliquoted into 0.75 mL (7.5 mg) tubes and stored at -20°C in the Investigational pharmacy at Duke.

On the day of NK cell-enriched DLI, for those patients who are randomized to receive DUK-CPG-001, 0.75 mL (7.5 mg) aliquots of DUK-CPG-001 will be dispensed to nurse, upon request, by the GMP facility personnel. DUK-CPG-001 will be thawed at room temperature right before use and a 5.0 mg dose will be injected intravenously right after

NK cell-enriched DLI. DUK-CPG-001 should be given as an IV push within 5 minutes of administration.

DNA oligonucleotides are very stable. A similar approved drug, Kynamro, is a DNA oligo and it can be left 30 degrees C for 14 days. Thus our plan is to use DUK-CPG-001 within 4 hours of thawing.

4.52 DUK-CPG-001 storage and accountability

Storage:

DUK-CPG-001 is stored at -20°C freezer until use in the Investigational Chemotherapy Services pharmacy at Duke.

Accountability:

The ICS is responsible for establishing study - specific procedures for appropriate drug accountability, billing, procurement, storage, preparation, dispensing and destruction of all investigational drugs within the Cancer Center. These procedures comply with local, state and federal requirements and are consistent with practice standards of the American Society of Health - System Pharmacists and the Joint Commission on Accreditation of Healthcare Organizations. Investigational drugs are accounted for using the National Cancer Institute's Investigational Drug Accountability Record (DAR). All drug transfers, receipts and disposal are recorded on the DAR. Prepared, but unused, IV medications will be destroyed in accordance with requirements of the principal investigator, the sponsor and applicable OSHA and EPA regulations. Documentation of destruction is made on the DAR.

4.53 DUK-CPG-001 transport and administration

Transport:

Study medications that are to be transported to another pharmacy in the hospital are transported by either a member of the Investigational Chemotherapy Service or by the Stem Cell Transplant Courier. If the medication is refrigerated or frozen, drug is transported with ice and immediately delivered to the appropriate satellite.

Administration:

Using standard institutional guidelines, 5.0 mg of DUK-CPG-001 will be injected intravenously right after the NK cell-enriched DLI. DUK-CPG-001 is expected to be stable within 4 hours of thaw.

4.54 Adverse effects of CPG7909, which is identical to DUK-CPG-001

The primary adverse events of CPG7909, which is identical to DUK-CPG-001, are dose-dependent local injection reactions (such as erythema, pain, swelling, induration, pruritus or warmth at the site of injection) when subcutaneously administered or systematic flu like reactions (such as headache, rigors, myalgia, pyrexia, nausea and vomiting) (Table 3).⁸⁴ The most commonly reported treatment-related hematologic toxicities are lymphopenia, leukopenia, neutropenia, anemia, and thrombocytopenia. Dyspnea, syncope, and hypotension are also reported.⁸⁵ Published >=Grade 3 adverse effects of CPG 7909 combined with or without any chemotherapy/radiotherapy are shown in Table 3.

Table 3A: Grade3/4 Adverse effect of CPG7909 (monotherapy)	Pashenkov, et al (Ref 51)	Weber, et al (Ref 53)	Thompson, et al (Ref 54)	Yamada, et al (Ref 56)	Kim, et al (Ref 59)	Link, et al (Ref 62)
	n=20	n=92	n=39	n=12	n=28	n=23
General disorders and administration site conditions						
Injection-site reactions			1 (3%)			1 (4%)
Fatigure			4 (10%)		4 (14%)	
Malaise			1 (3%)			
Pyrexia			1 (3%)			
Rigors			1 (3%)			
Asthenia		2 (2%)				
General physical health deteriorartion		2 (2%)				
Metabolism and Nutrition Disorder						
Anorexia			1 (3%)			
Hypophosphatemia			1 (3%)			
Dehydration		1 (1%)				
Gastrointestinal disorders						
Nausea		2 (2%)				
Vomiting		1 (1%)				
Nervous system disorders						
Dizziness					1 (4%)	
Memory impairment			1 (3%)			
Amnesia		1 (1%)				
Psychiatric disorders						
Confusion			1 (3%)			
Skin and subcutaneous tissue disorders						
Night sweats		1 (1%)				
Urticaria		1 (1%)				
Hematologic and lymphatic disorders						
Anemia		4 (4%)				3 (13%)
Leukopenia					1 (4%)	
Lymphopenia		5 (5%)		1 (8%)	4 (14%)	3 (13%)
Neutropenia	1 (5%)	2 (2%)			2 (7%)	2 (9%)
Febrile neutropenia		1 (1%)				
Thrombocytopenia					4 (17%)	
Laboratory value abnormalities						
Increased LDH		1 (5%)				
Increased ALT					1 (4%)	
Increased γ -GTP					1 (4%)	
Neoplasms benign, malignant and unspecified						
Chronic lymphatic leukemia		1 (5%)				
Ear and labyrinth disorders						
Deafness neurosensory		1 (5%)				
Musculoskeletal disorders						
Peripheral swelling		1 (5%)				
Back pain					2 (7%)	
Arthralgia			1 (3%)			
Muscle spasms			1 (3%)			
Myalgia			1 (3%)			
Polyarthralgia			1 (3%)			
Pain in extremity		2 (2%)				
Infections and infestations						
Pneumonia		1 (1%)				
Postprocedural site wound infection		1 (5%)				
Respiratory, thoracic, and mediastinal disorders						
Dyspnea		4 (4%)			1 (4%)	2 (9%)
Pleural effusion		2 (2%)				
Vascular Disorder						
Hypotension		1 (1%)	1 (3%)			
Renal and urinary disorders						
Potassium		1 (5%)				
Sodium		1 (5%)				
Uric acid		1 (5%)				
Coagulation						
PT		1 (5%)				
PTT		1 (5%)				
Immune system						
Anaphylaxis			2 (2%)			

Table 3B: Grade3/4 Adverse effect of CPG7909 (combination therapy including cytotoxic chemotherapy)	Weber, et al (Ref 53)	Manegold, et al (Ref 55)	Yamada, et al (Ref 56)	Manegold, et al (Ref 57)	Hirsh, et al (Ref 58)	Brody, et al (Ref 60)	Leonard, et al (Ref 61)
	W/cytotoxic chemo Tx	W/cytotoxic chemo Tx	W/cytotoxic chemo Tx	W/cytotoxic chemo Tx	W/cytotoxic chemo Tx	W/RadioTx	W/Rituximab
	n=45	n=75	n=12	n=393	n=384	n=15	n=31
General disorders and administration site conditions							
Injection-site reactions		5 (7%)	1 (8%)	41 (10%)	18 (5%)		
Fatigure		5 (7%)		31 (8%)	27 (7%)		
Pyrexia				7 (2%)	5 (1%)		
Weakness		3 (4%)					
Asthenia				16 (4%)	10 (3%)		
Flu-like symptoms			2 (17%)	18 (5%)	12 (3%)		
Constipation				2 (1%)	2 (1%)		
Peripheral edema				2 (1%)			
Metabolism and Nutrition Disorder							
Anorexia			2 (7%)	14 (4%)	8 (2%)		
Hypocalcemia						1 (3%)	
Hypokalemia						1 (3%)	
Dehydration		3 (4%)					
Gastrointestinal disorders							
Nausea	2 (4%)	2 (3%)		17 (4%)	13 (3%)		
Diarrhea		5 (7%)		10 (3%)	7 (2%)		
Vomiting	2 (4%)	1 (1%)		25 (6%)	8 (2%)		
Abdominal pain		2 (3%)					
Gastroesophageal reflux	1 (2%)						
Nervous system disorders							
Peripheral neuropathy		2 (3%)			23 (6%)		
Convulsions						1 (3%)	
Parathesia					2 (1%)		
Headache				4 (1%)	2 (1%)		
Psychiatric disorders							
Depression						1 (3%)	
Skin and subcutaneous tissue disorders							
Urticaria	1 (2%)						
Alopecia					12 (3%)		
Erythema					2 (1%)		
Rash				3 (1%)			
Hematologic and lymphatic disorders							
Anemia	3 (7%)	11 (15%)	3 (25%)	150 (38%)	57 (15%)	1 (3%)	
Leukopenia	5 (11%)	36 (48%)	7 (58%)	208 (53%)	159 (41%)		
Lymphopenia	9 (2%)	18 (24%)	4 (33%)	87 (22%)	92 (24%)	1 (3%)	
Neutropenia	4 (9%)	54 (72%)	11 (91%)	291 (74%)	281 (73%)	2 (6%)	
Febrile neutropenia	2 (4%)	3 (4%)					
Infections		1 (1%)					
Thrombocytopenia	2 (4%)	14 (19%)	2 (17%)	267 (68%)	66 (17%)		
Hemoptysis		2 (3%)					
Blood production transfusion						1 (3%)	
Laboratory value abnormalities							
Hepatic function abnormal						1 (3%)	
Hyperbilirubinemia						1 (3%)	
Neoplasms benign, malignant and unspecified							
Malignant neoplasm progression						1 (3%)	
Musculoskeletal disorders							
Back pain				11 (3%)			
Arthralgia				9 (2%)			
Myalgia				2 (1%)			
Pain in extremity			8 (2%)	8 (2%)		1 (3%)	
Infections and infestations							
Bacteremia						1 (3%)	
Cardian disorders							
Cardiac failure						1 (3%)	
Chest pain				8 (2%)			
Respiratory, thoracic, and mediastinal disorders							
Dyspnea	2 (4%)			30 (8%)		1 (3%)	
Pleural effusion	1 (2%)						
Cough				5 (1%)	5 (1%)		
Vascular Disorder							
Hypertention						1 (3%)	
Deep venous thrombosis						2 (6%)	
Renal and urinary disorders							
Ureteric obstruction						1 (3%)	
Urinary retention						1 (3%)	
Acute renal failure						1 (3%)	
Coagulation							
PTT						1 (3%)	

4.6 Dose delays and modifications

4.6.1 Delayed NK cell-enriched DLI and DUK-CPG-001 administration

Due to clinical concerns for the patients such as concern over GVHD, infection, or other clinical reasons, the NK cell-enriched DLI with or without DUK-CPG-001 may be altered by up to \pm 4 weeks. However, the NK cell-enriched DLI will not be administered earlier than 4 weeks post transplant.

5.0 PATIENT REGISTRATION

All patients must be registered with the study coordinator and data coordinator. The eligibility checklist must be complete and the IRB approved consent form signed before any protocol therapy may be started on the patient or donor.

6.0 STUDY DESIGN AND ANALYSIS

This is a randomized, parallel phase II study of NK cell-enriched DLIs when administered alone or administered with the TLR9 agonist, DUK-CPG-001, from a 7-8/8 HLA-matched related/unrelated donor (Cohort A) or 4-6/8 HLA-matched related donor (Cohort B) following allogeneic stem cell transplantation.

In Cohort A, a total of 50 patients will be randomized with equal allocation to two arms defined by whether or not a TLR9 ligand, DUK-CPG-001, is administered with NK cell-enriched DLIs. In Cohort B, a total of 50 patients will be randomized with equal allocation to the two arms. Stratification will be done within disease types (myeloid or lymphoid diseases) in each cohort. A block randomized design is used to randomize patients to the two treatments within each stratum for each cohort. Primary endpoints are analyzed separately in Cohort A and B.

6.1 Primary Objectives 1 and 2

1. To evaluate the one-year progression-free survival rates in patients receiving NK cell-enriched DLI administered alone from a 4-6/8 HLA-matched related or 7-8/8 HLA-matched donor following allogeneic stem cell transplantation.
2. To evaluate the one-year progression-free survival rates in patients receiving NK cell-enriched DLI administered with a TLR9 ligand, DUK-CPG-001, from a 4-6/8 HLA-matched related or 7-8/8 HLA-matched donor following allogeneic stem cell transplantation

6.1.1 Definition of progression-free survival

Progression-free survival is defined from the day of the first NK cell-enriched DLI until the day of disease relapse, disease progression, or death whichever comes first. Patient without relapse, progression, or death will be censored at the last follow-up.

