4.3 Patient Evaluation

- 4.3.1 Patients must remain in clinic for at least 2 hours post-infusion for observation.
 - Vital signs must be checked every 30 minutes

- 4.3.2 Assessment of disease will use standardized criteria and shall include a careful examination of the studies needed to detect the disease (for example, PET, radiographs, immuno-phenotype, marrow, molecular studies etc.).^{77, 78, 79, 80, 81, 82} Restaging may be altered at the discretion of the transplant physician following the patient (who are all subinvestigators in this study) if the patient is felt to be progressing before these time points but the recommended restaging is 3,6, and 12 months for 1 year after the last NK-enriched DLI, q6 months for the next 2 years, then as indicated clinically.
 - ❖ Assessment of disease is required prior to each NK cell-enriched DLI, and 3,6, and 12 months for 1 year after the last NK-enriched DLI, then q6 month for the next 2 years.
 - ❖ Immune reconstitution studies prior to and 1 day and 1 month after each NK cell-enriched DLI, and 3, 6, and 12 months after the last NK-enriched DLI.
 - ❖ Determination of chimerism (by short tandem repeat analysis in use in our DUKE HLA laboratory with a 2% sensitivity) just prior to each NK cell-enriched DLI, and 3, 6, 12 months after the last NK-enriched DLI.

- 4.3.3 Toxicity will be formally evaluated by the protocol investigators, health care professionals directly under the supervision of protocol investigators, or physicians specifically trained in hematopoietic cell transplant will monitor the subjects' safety at appropriate intervals up until at least two years after NK infusion. Monitoring will occur 1 day post infusion and 1 month later (more as determined by treatment team) and, then 3, 6, and 12 months post-second DLI for the first year post-second DLI.

Assessments performed include the following for toxicity assessment following the NCI common toxicity criteria (version 4) and standard GVHD criteria (appendix I).:
 - Medical history (specific to GI toxicity as well as overall new problems),
 - Physical exam,
 - CBC,
 - Liver function tests (AST, ALT, bilirubin at a minimum), and
 - Chemistry CS to include creatinine and BUN

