6.1.2 Statistical considerations

Cohort A (7-8/8 HLA-matched related or unrelated transplantation)

A 2-stage MiniMax design⁸⁶ will be used to test the null hypothesis that the progression-free survival rate is \leq 46% against the alternative hypothesis that it is \geq 71% in each arm. Nine patients will be treated in the first stage. If the number of patients who are alive without relapse/progression is equal to 4 or less at 1 year after transplantation in one arm, then the study for the arm will be terminated and the treatment is ineffective. If there are at least 5 patients (56%) who are alive without relapse/progression at 1 year after transplantation, the sample size will be increased up to a maximum of 25 patients. If the number of patients who are alive without relapse/progression is

equal to 15 or less at 1 year after transplantation, then the treatment is ineffective. If there are at least 16 patients (64%) who are alive without relapse/progression at 1 year after transplantation, this protocol will be deemed effective. This design has a significance level of 0.05, a power of 0.80, a probability of early termination under the null of 0.60, and an expected sample size under the null of 16 patients.

Table 4

Stage	Total Accrual	Close study/therapy if number of patients who are alive without relapse/progression is \leq
1	9	4 (44%)
2	25	15 (60%)

Cohort B (4-6/8 HLA-matched related transplantation)

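### PFS is censored at the last follow-up rather than the last disease assessment, and no rule classifies patients at 1 year whose event-free status was not checked by restaging

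*Combined protocol and SAP*

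**What the plan says.** Section 6.1.1 sets the origin and the events: "Progression-free survival is defined from the day of the first NK cell-enriched DLI until the day of disease relapse, disease progression, or death", whichever is first. For everyone else it says "Patient without relapse, progression, or death will be censored at the last follow-up". The term is not defined and is not tied to a disease assessment.

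Section 6.1.2 then decides each arm by a count. For Cohort A: "If there are at least 16 patients (64%) who are alive without relapse/progression at 1 year after transplantation, this protocol will be deemed effective". Cohort B uses the same construction with 13 of 25. The documents do not say how to classify a patient who has no disease assessment at or after that time point.

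Section 4.3.2 requires disease assessment before each DLI, at 3, 6 and 12 months after the last DLI, and then every 6 months for 2 years. It describes the same timetable once as a recommendation and once as a requirement. Section 4.3.3 covers safety: clinicians "will monitor the subjects' safety at appropriate intervals up until at least two years after NK infusion". It adds unscheduled visits for toxicity, and a note that patients who do not receive the second DLI are followed every 3 months after the first.

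**The concern.** Relapse and progression are found by marrow, imaging and molecular studies. A clinic contact without them shows that the patient is alive and not overtly relapsed, but it does not establish freedom from progression. A rule that ends event-free time at the last contact therefore credits time in which progression may have gone unseen.

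Section 6.1.1 is the only text on how long a patient counts as event-free, so it is the natural guide when someone applies the count in 6.1.2. If it is used that way, errors run towards success. The test compares each arm with a fixed historical rate, the arms have at most 25 patients, and the attained type I error is already close to 0.05. If it is not used that way, classification is left to be settled during the trial, with the boundary in view.

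**Working it through.** **1. Reproduce the design.** Inputs from 6.1.2: Cohort A n1 = 9, r1 = 4, n = 25, r = 15, p0 = 0.46, p1 = 0.71; Cohort B n1 = 12, r1 = 4, n = 25, r = 12, p0 = 0.34, p1 = 0.59. The probability of declaring an arm effective at true rate p is

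R(p) = Σ (x = r1+1 to n1) Pr[Bin(n1, p) = x] × Pr[Bin(n − n1, p) ≥ r + 1 − x].

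| | R(p0) | R(p1) | Early stop under null | Expected n under null |
|---|---|---|---|---|
| A, computed | 0.0485 | 0.803 | 0.598 | 15.4 |
| A, stated | 0.05 | 0.80 | 0.60 | 16 |
| B, computed | 0.0456 | 0.802 | 0.612 | 17.0 |
| B, stated | 0.05 | 0.80 | 0.61 | 17 |

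The plan's figures reproduce. No censoring or dropout term enters the calculation.

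**2. Are there contacts past the landmark without required restaging?** Section 4.4.1 places the first DLI 1–6 months after transplantation and the second 1–3 months after the first. The last DLI therefore falls 1–6 months after transplantation (one DLI) or 2–9 months (two). One year after transplantation then lies 12 − 6 = 6 to 12 − 1 = 11 months after a single DLI, or 12 − 9 = 3 to 12 − 2 = 10 months after the second, before the ±4-week allowance in 4.6.1. The 12-month restaging always comes after the landmark.

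Example: first DLI at month 4 after transplantation and no second DLI. The 6-month restaging is at month 10 and is clear. The 3-monthly follow-up brings the patient back 9 months after the DLI, at month 13, with no restaging required. The patient is then lost. Section 6.1.1 censors at month 13, past the landmark, although the last required look for disease was at month 10. The same holds for any single DLI from month 3 to just before month 6. An ad hoc toxicity visit after a missed restaging has the same effect in any patient.

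**3. Sensitivity of type I error.** Let m be the share of true 1-year failures counted as successes. The documents give no value, so 2% and 5% are assumptions. The apparent null rate is p0 + (1 − p0)m.

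| m | A: apparent p0 | A: type I error | B: apparent p0 | B: type I error |
|---|---|---|---|---|
| 0 | 0.460 | 0.049 | 0.340 | 0.046 |
| 2% | 0.46 + 0.54 × 0.02 = 0.471 | 0.060 | 0.34 + 0.66 × 0.02 = 0.353 | 0.061 |
| 5% | 0.46 + 0.54 × 0.05 = 0.487 | 0.082 | 0.34 + 0.66 × 0.05 = 0.373 | 0.091 |

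In a full arm of 25, m = 5% is less than one patient on average: 25 × 0.54 × 0.05 = 0.68 in A and 25 × 0.66 × 0.05 = 0.83 in B.

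**4. The opposite classification.** Let u be the share of event-free patients with no assessment at or after the landmark, all counted as non-successes. The apparent alternative rate is p1(1 − u).

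| u | A: apparent p1 | A: power | B: apparent p1 | B: power |
|---|---|---|---|---|
| 0 | 0.710 | 0.803 | 0.590 | 0.802 |
| 2% | 0.71 × 0.98 = 0.696 | 0.758 | 0.59 × 0.98 = 0.578 | 0.768 |
| 5% | 0.71 × 0.95 = 0.675 | 0.684 | 0.59 × 0.95 = 0.561 | 0.710 |

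Both choices move the operating characteristics materially at small shares, so the choice has to be made in advance.

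**The case against.** The strongest reply is that the censoring sentence does not drive the primary decision. Section 6.1.2 counts patients and uses no Kaplan–Meier estimate, so changing the censoring date alone leaves every design figure as it is. That is correct. A reader might infer that the sentence makes unrestaged patients successes, and that the error always favours the treatment. The documents do not support that: they are silent on classification, and such patients could equally be counted as failures or excluded. What stands is that the only written rule points towards success and nothing in 6.1.2 overrides it.

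A reader might also take "Restaging may be altered at the discretion of the transplant physician following the patient" as permission to skip restaging. The sentence goes on to limit this to patients thought to be progressing before the planned times, which favours earlier detection.

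Nor is safety follow-up a generally denser stream. After month 1, scheduled toxicity visits following the second DLI fall at 3, 6 and 12 months, the same as restaging. The gap arises for patients followed every 3 months after a single DLI and at unscheduled visits. A note to Appendix V gives 3-monthly restaging, which would close the month-9 gap, but that appendix says the full protocol takes precedence over its chart.

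Finally, visits include examination and blood counts, so some relapses would be noticed without restaging, and a later clear restaging confirms status at the landmark. Both limit how often the problem would arise.

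**Conclusion.** The point holds in a limited form. Section 6.1.1 uses the wrong date for an endpoint that depends on assessment, and 6.1.2 lacks a rule for patients whose status at the landmark was not verified. Together they allow unverified patients to be counted as event-free. They do not require it, and the documents do not show how often it would occur.

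The rise in type I error to 0.060–0.082 (A) and 0.061–0.091 (B) is conditional on an assumed 2–5% misclassification of true failures. It is not an estimate of bias in this trial. The month-9 example also depends on the landmark being 1 year after transplantation, as 6.1.2 states. If the landmark ran from the first DLI, as 6.1.1 implies, that visit would precede it, and the remaining route would be a missed restaging followed by another contact. The change is worth making before data are reviewed; the design figures need no correction.

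**What to change.** 1. In 6.1.1, censor patients without an event at the date of the last disease assessment under 4.3.2 that shows no relapse or progression.
2. In 6.1.2, treat a patient as a confirmed success only if a disease assessment at or after the 1-year landmark shows no relapse or progression. Accept any such assessment, including the later scheduled 12-month post-DLI restaging; no visit window exists at 1 year after transplantation, so a narrow window would fail patients who were restaged on schedule.
3. Report the boundary count with unverified patients as non-successes, and a sensitivity count with them as successes.
4. Reconcile the three time origins (first DLI in 6.1.1, transplantation in 6.1.2, last DLI in 4.3.2) so that the landmark is unambiguous.

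The text change is small and adds no procedure, but it has two costs. Each unverified patient lowers the observed rate: power falls to about 0.76 (A) and 0.77 (B) with 2% of event-free patients unverified, and to 0.68 and 0.71 with 5%, so completeness of restaging should be tracked. Confirmation can also come after the landmark. With the last DLI just before month 6 after transplantation, the 6-month restaging falls just before month 12 and the next is just before month 18, a wait of nearly 6 months that also affects the stage 1 decision.
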